### Risk/Benefit Assessment

Risks: It is possible that the patient may abrade the cornea during a measurement resulting in a corneal abrasion. The likelihood of such an event occurring with the Eye Check tonometer is remote due to the disposable probe cover made out of contact lens material (thus protecting the cornea) during the measurement. Pain, redness, watering, and blurry vision are symptoms that would alert the patient immediately and they will be instructed to contact the principal investigator and stop the study. Such abrasions typically heal within 24-48 hours unless the patient is a diabetic in whom it may take longer and thus a history of diabetes is an exclusion factor. There is a remote possibility that the corneal abrasion can get infected.

Sanitation of device - The head of the unit will be bent so that the entire tip will be dipped in the standard cleaning solutions (those used for Goldmann tonometer tips), then dried (per the current

protocol), and then used on any subsequent patient in the study. The actual device will be wiped down with cavi wipe per standard clinic protocols.

Benefits: The physician will be able to assess the accuracy of the IOP measurements with the Eye Check tonometer, which has the potential to be used as a device by which the patients can check their own IOP at home in the future. This may lead to better management of their glaucoma.

#### Data Analysis & Statistical Considerations

The IOP readings from the Eye Check tonometer and the Goldmann will be compared. The Goldmann measurements are typically considered the gold standard. Mean IOP and standard deviation of IOP measurements using the two devices will be assessed.

If needed, for correlation analyses, data such as age, pachymetry, refractive error, etc., will be obtained by the clinical investigators from the charts.

The data of the Eye Check tonometer, which, as mentioned above, does not contain any subject identification or IOP data, will be analyzed. The IOP, Standard of Measurement, number of successful readings, and performance scores will be derived.

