## Purpose of the Study

To investigate whether the new applanation tonometer (Eye Check monitor) can provide intraocular pressure (IOP) measurements comparable to those of traditional tonometers such as the Goldmann applanation tonometer.

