## Design & Procedures

Prospective consecutive series of 50 adult patients. Consecutive patients coming to the Duke Eye Center will be approached by a research coordinator for the possibility of participating in the study. Subjects will be screened based on the inclusion and exclusion criteria (Selection of Subjects section). Eligible and willing patients will be asked to sign the consent form for the study.

Participants will be assigned a unique code number. The key to this code will be in a locked key file with the principal investigator. Both eyes will be evaluated in this study. The user (patient) will then be informed by a skilled technician, who is experienced with use of the Eye Check tonometer, on how to use it by themselves.

The subject will perform a self-alignment procedure that trains for alignment and assesses the results. During this procedure, no contact will be made with the probe. The progress will be monitored and recorded. Only subjects who pass the alignment criteria will proceed to obtain IOP measurements. Prior to the instillation of any eye drops, five immediately consecutive readings will be obtained with the Eye Check tonometer. Each of these readings will be recorded in the Eye Check tonometer connected computer without any subject identifier other than the identification code. IOP measurements by a certified ophthalmic technician using the Goldmann Applanation tonometer, within 5 minutes after the use of the Eye Check tonometer will be performed. Other data such as age, pachymetry, refractive error, etc., will be recorded.

Patients will be provided with a questionnaire to assess comfort and ease of use.

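### The device comparison is not stated as within-eye, and reading success is not related to the same eye's Goldmann pressure, so failures concentrated at high IOP could go unseen

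*Combined protocol and SAP*

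**What the plan says.** The aim (Purpose of the Study) is to find out whether the new device "can provide intraocular pressure (IOP) measurements comparable to those of traditional tonometers such as the Goldmann applanation tonometer". Under Design & Procedures the study is a "Prospective consecutive series of 50 adult patients", and "Both eyes will be evaluated in this study". A no-contact alignment test comes first: "Only subjects who pass the alignment criteria will proceed to obtain IOP measurements". Then "five immediately consecutive readings will be obtained with the Eye Check tonometer", and a technician takes the Goldmann measurement "within 5 minutes after the use of the Eye Check tonometer will be performed". The device description in Background & Significance mentions quality control once the IOP has been derived, but gives no pass or fail rule.

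Under Data Analysis & Statistical Considerations, "The IOP readings from the Eye Check tonometer and the Goldmann will be compared", and the only summaries named for that comparison are the mean and SD of IOP for each device. The same section adds: "The IOP, Standard of Measurement, number of successful readings, and performance scores will be derived". Correlation analyses are optional; the covariates named are age, pachymetry and refractive error, in a list left open.

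No section defines a successful reading, sets a minimum number per eye, says how an eye with few or no successes enters the comparison, states that values are paired within eye, or links success to Goldmann IOP.

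**The concern.** By deriving a count of successful readings, the plan allows for some of the five failing. A failed reading presumably has no usable IOP. The plan does not say that failures are dropped, but it gives no other handling.

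Two separate problems can follow if failure is more common at high pressure.

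- **Weighting.** If raw readings are pooled, an eye with five successes counts five times and an eye with one counts once, while each eye's Goldmann value counts equally. The two device means then describe different mixes of eyes.
- **Selection.** Even with a correct within-eye comparison, agreement is described only for eyes that gave at least one usable reading. An overall success count does not show whether the missing readings come from the eyes with high pressure.

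The second matters more. Background & Significance justifies home tonometry by the IOP peaks that office readings miss. A device that reads poorly or not at all at high pressure would fall short of that purpose, and the listed summaries need not show it.

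**Working it through.** The plan gives no SD, margin, power or failure rate, so there is no stated figure to reproduce. The check asks how large each problem could be.

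**Inputs from the documents (Design & Procedures).** 50 patients, both eyes (50 × 2 = 100 eyes), five Eye Check readings.

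**Assumed inputs.** Goldmann IOP X ~ N(16, 4²) mmHg; an accurate device; success probability p(x) logistic in x, 95% at 12 mmHg and 80%, 60% or 30% at 26 mmHg; the five readings in an eye succeed or fail independently given x.

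**Step 1, slopes.** b = [logit p(26) − logit 0.95] / 14, with logit 0.95 = 2.944:

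- 80%: (1.386 − 2.944)/14 = −0.111 per mmHg
- 60%: (0.405 − 2.944)/14 = −0.181
- 30%: (−0.847 − 2.944)/14 = −0.271

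**Step 2, pooled readings.** Each eye is weighted by its expected successes, so the shift is E[X·p(X)]/E[p(X)] − 16 = Cov(X, p)/E[p], by numerical integration:

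- 80%: −0.132/0.918 = −0.14 mmHg
- 60%: −0.282/0.884 = −0.32 mmHg
- 30%: −0.542/0.822 = −0.66 mmHg

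**Step 3, one mean per eye, unpaired.** An eye contributes if it has at least one success, with probability q(x) = 1 − (1 − p(x))⁵. The shift is E[X·q(X)]/E[q(X)] − 16.

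| Success at 26 mmHg | Overall success | Pooled shift (mmHg) | One mean per eye (mmHg) | Eyes with no success |
|---|---|---|---|---|
| 80% | 91.8% | −0.14 | 0.000 | 0.002% |
| 60% | 88.4% | −0.32 | −0.003 | 0.04% |
| 30% | 82.2% | −0.66 | −0.05 | 0.6% |

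**Step 4, paired within eye.** For an accurate device the expected Eye Check minus Goldmann difference is zero at every x, so it stays zero whichever eyes are lost through x.

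**Step 5, what the overall count hides.** In the 30% case, eyes at 22 mmHg or more are 6.7% of eyes (about 7 of 100) but supply 3.6% of successful readings. They average 2.2 successes out of five, against 4.2 in the other eyes. The overall figure is still 82%.

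**Step 6, selection under harsher failure.** A separate simulation used 4,000 replicates of 50 patients, two eyes and five readings. Its assumptions were true IOP mean 17, SD 5 mmHg; between-eye correlation 0.8; Goldmann error SD 1.5; Eye Check per-reading SD 2.5. Failure was flat at 20%, rose logistically around 24 mmHg, or was 95% or 100% at 25 mmHg and above (10% below).

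- Accurate device: with 100% failure at 25 mmHg and above, 70% of eyes with Goldmann IOP of 25 mmHg or more had no Eye Check value, yet the paired difference was 0.0 mmHg (SD 1.9). Unpaired per-eye means differed by 0.2 to 0.6 mmHg across the three IOP-dependent patterns.
- Device under-reading by 0.4 mmHg per mmHg above 21: the paired bias was −0.24 mmHg with no failures, and −0.20, −0.15 and −0.11 under the three IOP-dependent patterns.
- The correlation between failed readings and the same eye's Goldmann IOP was 0.00 under flat failure and 0.36 to 0.64 when failure rose with IOP. Eyes with no reading were 23% to 70% at 25 mmHg or more, against 0% to 1% below. The added tabulation would therefore show the pattern.

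**The case against.** The strongest reply is that the 0.14 to 0.66 mmHg figures need raw readings to be pooled, which the plan never says. It lists IOP in the singular beside a reading count, which reads at least as naturally as one IOP per session. With one mean per eye the shift almost vanishes in Step 3, and with pairing it is zero. This stands, although Step 3 relies on independent failures within an eye; failures that cluster in the same eyes would remove more of them.

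A reader might infer that the mean difference is biased even for a perfectly accurate device. The documents do not support that. It holds only for pooled readings or unpaired means, and the plan commits to neither. A reader might also infer that a device failing at high pressure will be made to look comparable. The weighting effect does the opposite: it makes an accurate device read low. Concealment needs a device that is also inaccurate at high pressure. The changes in paired bias found for that case (−0.24 to between −0.20 and −0.11 mmHg) are small, and the plan has no agreement margin against which to judge them.

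The premise is also conditional. Nothing in the documents shows that failure depends on IOP, and the alignment and contact steps point just as readily to user-related failure. Nor is the check excluded: the covariate list is open and the undefined performance scores might capture some of it. High-IOP eyes will be few, so a regression would be imprecise. All of this stands. It limits the size and certainty of the point, but it leaves the pairing rule and the link between success and Goldmann IOP unstated.

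**Conclusion.** The point holds as a conditional risk with a cheap remedy. The plan specifies neither a within-eye comparison nor any relation between reading success and Goldmann IOP.

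If success falls with IOP, the weighting bias for an accurate device is 0.14 to 0.66 mmHg with pooled readings, 0.00 to 0.05 mmHg with one mean per eye, and zero in expectation when paired. These figures rest on the assumed N(16, 4²) distribution, the assumed success curves and independent failures within an eye.

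The selection problem survives pairing. Its main harm is not a large shift in a mean but an agreement result that says nothing about the eyes the device could not read.

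It should not be assumed that the plan already secures Goldmann values for those eyes. The timing statement places Goldmann after Eye Check use and is silent on what happens when every attempt fails.

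**What to change.** Amend Data Analysis & Statistical Considerations as follows.

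1. Make the comparison within eye: one Eye Check value per eye against that eye's Goldmann value, eyes equally weighted, with clustering by patient. State how the single value is formed and what counts as a successful reading.
2. Tabulate successes out of five, and eyes with no usable reading, by Goldmann IOP. Add a logistic model of successes on Goldmann IOP, clustered by patient, as exploratory support only, because about 7 of 100 eyes would be at 22 mmHg or more under the assumptions above.
3. Beside the agreement result, report the number and Goldmann IOP of attempted eyes with no usable Eye Check value. If an agreement limit is set in advance, count those eyes as not in agreement. The plan has no such limit at present.

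In Design & Procedures, confirm that the planned Goldmann measurement is recorded for every attempted eye, including those where all Eye Check readings fail.

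The cost is a few sentences and a little code, with no new visits provided Goldmann is taken in every attempted eye. The reported agreement may look slightly less favourable.

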## Background & Significance

Glaucoma is a disease that is usually caused by increased pressure in the eye which damages the optic nerve. It is a leading cause of blindness for people over 60 years old. Blindness from glaucoma can often be prevented with early treatment. The global prevalence of glaucoma for population aged 40-80 years is 3.54 percent. In 2013, the number of people (aged 40-80 years) with glaucoma worldwide was estimated to be 64.3 million, increasing to 76.0 million in 2020 and 111.8 million in 2040. The damage to the optic nerve can be prevented or slowed down by reducing the intraocular pressure (IOP). The ophthalmologist bases his/her decisions on IOP readings performed in the office with a tonometer. However, the values obtained during office hours have been shown to be unable to identify IOP peaks and variations. Therefore, IOP measurements in the office provide limited and potentially misleading information in planning the management of new patients and the evaluation of drug therapy or surgery intervention in patients already under care. Moreover, studies have shown that short-term IOP fluctuations and inter-visit IOP variations are prognostic factors for glaucoma progression. Therefore IOP monitoring by the patients, in their natural environment, referred to as home or self-tonometry, would provide reliable data of clinical importance for the management of glaucoma.

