The Goldmann applanation tonometer is the gold standard for measuring the IOP. It measures the force necessary to flatten (applanate) the central cornea. As shown in the figure, to perform a measurement the subject is seated in front of a slit-lamp microscope. The operator places a drop of fluorescent dye and anesthetic on the eye and asks the patient to look straight ahead, open both eyes wide, fix his/her gaze and keep perfectly still. The operator gently holds up the patient's top eyelid, taking care not to put any pressure on the eye and moves the tonometer forward and perpendicular to the cornea until the prism rests gently on the center of the subject's cornea. With the other hand, the operator turns the calibrated dial on the tonometer thereby increasing the force applied by the probe on the cornea. The operator continues to increase the force until the tear film at the periphery of the probe (seen as a fluorescent ring) reaches a preset diameter. The probe is then withdrawn from the eye and the value on the dial, corresponding to the force necessary to flatten the cornea (calibrated in mmHg units of IOP) is recorded in the notes. The calibration takes into account the force to deform the cornea when the IOP is absent and the opposite capillary force generated by the meniscus of fluid.

Despite the availability of self-tonometers and the proof of their clinical value, IOP monitoring by patients, in their own environment, has not been used widely. As stated in the Liang review, the economical hurdles have prevented the commercialization of this technology: the lack of reimbursement for the instrument cost (e.g. \$2150 for the iCare Home tonometer <https://www.howmuchisit.org/icare-tonometer-cost/>), the training of the patient and data processing has deterred clinicians from implementing IOP home monitoring in their routine clinical practice. The

experience so far indicates that, to be adopted clinically for IOP monitoring, a self-tonometer must be: usable by most patients, require no corneal anesthetic, safe, require no or minimal training by ophthalmologists' clinical staff and capable to yield values that correlate well with gold standard tonometry.

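### The only statistics named for comparing Eye Check with Goldmann are mean IOP and SD; these show average bias at most, so if the analysis stops there it cannot support a claim of comparability

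*Combined protocol and SAP*

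**What the plan says.** The Purpose of the Study is to find out whether the new device "can provide intraocular pressure (IOP) measurements comparable to those of traditional tonometers such as the Goldmann applanation tonometer". No numerical criterion is attached to that aim.

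The Data Analysis & Statistical Considerations section is the whole analysis plan. It opens with a general statement, "The IOP readings from the Eye Check tonometer and the Goldmann will be compared", and then names the statistics: "Mean IOP and standard deviation of IOP measurements using the two devices will be assessed". Two further sentences might seem relevant:

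- "If needed, for correlation analyses, data such as age, pachymetry, refractive error, etc., will be obtained by the clinical investigators from the charts". This is conditional and concerns chart covariates.
- "The IOP, Standard of Measurement, number of successful readings, and performance scores will be derived". These quantities come from the Eye Check data alone, and the Standard of Measurement is not defined.

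In Background & Significance, a self-tonometer is required to be "capable to yield values that correlate well with gold standard tonometry". That is a requirement on devices, not an analysis.

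Under Design & Procedures, both eyes of 50 patients are measured: five Eye Check readings first, then Goldmann no more than 5 minutes later. Only patients who pass the alignment step are measured. No section names paired differences, limits of agreement or a tolerance.

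**The concern.** Two devices can have the same mean and the same SD and still disagree badly on individual eyes, because errors in opposite directions cancel in the averages. The aim concerns whether one device's reading can stand for the other's, and that depends on the size of the differences within each eye. If the report gives only a mean and an SD per device, close and poor agreement look alike, and the study's single stated question goes unanswered although the data to answer it were collected. With no tolerance fixed in advance, the meaning of comparable would also be open to choice after the results are known.

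**Working it through.** **Inputs.** From the documents: 50 subjects, two eyes each, five Eye Check readings, Goldmann second. The plan has no SD, correlation, margin or sample-size calculation, so there is no figure to reproduce. Assumed: SD of IOP across patients 4 mmHg (range 3 to 5), equal on both devices; equal means; correlation r between devices 0.6 to 0.95.

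**Step 1: what means and SDs determine.** The mean difference is the difference of the two means. The SD of the within-eye differences is SDd = √(s1² + s2² − 2·r·s1·s2). The device SDs s1 and s2 do not fix r. They only bound SDd between |s1 − s2| and s1 + s2, which is 0 to 8 mmHg when both are 4.

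**Step 2: size.** With equal SDs, SDd = SD·√(2(1 − r)), and the 95% limits of agreement are ±1.96·SDd around zero bias. At SD 4:

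| r | SDd (mmHg) | 95% limits (mmHg) |
|---|---|---|
| 0.95 | 1.26 | ±2.5 |
| 0.9 | 1.79 | ±3.5 |
| 0.8 | 2.53 | ±5.0 |
| 0.6 | 3.58 | ±7.0 |

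All four rows give the same table of means and SDs. Across SD 3 to 5 the range is ±1.9 (SD 3, r 0.95) to ±8.8 (SD 5, r 0.6).

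**Step 3: direct check.** One set of 50 simulated values (mean 17.86, SD 3.56) was used for both devices and paired in three ways. Means and SDs stay identical. The limits were 0 with perfect pairing, ±9.2 with random pairing and ±13.9 with reversed pairing. The last two show the algebra and are not realistic scenarios.

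**Step 4: the other meaning of SD.** If the SD is the spread of repeated readings on one eye, it measures one device's repeatability. It still says nothing about the spread of differences between devices. The conclusion is the same under either meaning; only the illustration in Step 2 uses the first.

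**Step 5: would a device-to-device correlation fill the gap?** For fixed SDd = 2.53 (SDd² = 6.4), r = 1 − 6.4/(2·SD²). This is 0.64, 0.80 and 0.87 at SD 3, 4 and 5. The same ±5.0 limits thus give quite different correlations depending on how varied the patients are, and a constant offset leaves r unchanged.

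**Step 6: precision of the limits.** With one eye per subject, the 95% CI half-width of a limit is t·SDd·√(1/n + 1.96²/(2(n − 1))). At n = 50: 2.01 × √(0.0200 + 0.0392) = 0.489, times 2.53 = 1.24 mmHg. The outer bound is then 4.96 + 1.24 = 6.20, or 1.25 times the point limit. With both eyes modelled, t·SDd·√((1 + ρ)/(2n) + 1.96²(1 + ρ²)/(4n)) gives 0.94, 1.00 and 1.09 mmHg for a between-eye correlation of differences ρ of 0.3, 0.5 and 0.7 (assumed).

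**Step 7: how strict an outer-bound rule would be.** Simulated with 50 subjects, one eye each and SDd 2.53. If the true limits equal the tolerance and bias is zero, the point limits fall inside it about 32% of the time and the outer confidence bounds about 1%. With true limits of ±5.0 around the bias and a tolerance of 7.0 mmHg (7.0/4.96 = 1.41), the outer bounds pass 80% of the time at zero bias, 68% at 0.5 mmHg bias and 41% at 1 mmHg bias.

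**The case against.** The strongest reply is that this is a gap in specification, not in design. The plan says in general terms that readings will be compared, both devices are used on the same eyes minutes apart, and nothing confines the analysts to two summaries. That stands, and it is why the point is conditional. A reader might infer that the plan rules out a paired analysis or that the data cannot answer the question; the documents support neither. What the reply does not remove is that the only statistics named cannot answer the stated question, and that a method and tolerance chosen after the data are seen would weaken any claim of comparability.

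A reader might also rest the need for agreement on the statement that "short-term IOP fluctuations and inter-visit IOP variations are prognostic factors for glaucoma progression". That link is loose. Fluctuation is change within a patient; a stable offset in one eye cancels when change is tracked, and repeatability then matters more. Limits of agreement mix stable offset with random error. The need for agreement follows from the Purpose of the Study and requires no more.

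Finally, one might conclude that the outer confidence bounds must lie inside the tolerance. That is one defensible rule, not the only one, and Step 7 shows its severity. Estimation with confidence intervals read against a fixed tolerance also closes the gap.

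**Conclusion.** The point holds in this conditional form and should be fixed before analysis, since it affects the only comparison serving the only stated purpose. The named statistics give average bias at most. If the analysis stops there, the same table fits limits from ±2.5 to ±7.0 mmHg at an assumed SD of 4, and from ±1.9 to ±8.8 over SD 3 to 5, with r between 0.95 and 0.6 throughout. The magnitudes rest on those assumed values; the conclusion does not, because it follows from the formula for SDd whatever the values are.

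**What to change.** In the Data Analysis & Statistical Considerations section, make a paired agreement analysis primary:

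1. For each eye, take the mean of the successful Eye Check readings minus Goldmann.
2. Report mean bias and 95% limits of agreement, each with a 95% CI that allows for two eyes per subject (mixed model), or use one pre-specified eye.
3. Before the data are seen, the investigators fix a tolerance in mmHg against which the limits and their CIs are read, and report the share of eyes within it. Requiring the outer confidence bounds to lie inside the tolerance is an optional stricter rule.
4. Plot differences against pair means. Keep means, SDs and correlations as descriptive.
5. Limit the conclusion to subjects who pass alignment and report how many do not. Because Eye Check always precedes Goldmann, state that the estimated bias includes any order effect.

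**Cost.** No new measurements are needed. Eye Check readings are stored "without any subject identifier other than the identification code", so pairing relies on that code, and the file must also show which eye was read. The extra analysis is modest, and the result may look less favourable than a comparison of means. The limits will be uncertain by about ±1.2 mmHg each (50 subjects, one eye, SD 4 and r 0.8 assumed). If the outer-bound rule is adopted, an 80% chance of passing needs a tolerance about 1.4 times the true limits at zero bias, and a larger one if there is bias.

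### The plan does not say how the five Eye Check readings enter the comparison with Goldmann, and mean and SD by device cannot show paired agreement or the error of a single self-reading

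*Combined protocol and SAP*

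**What the plan says.** Under Design & Procedures, the study is a "Prospective consecutive series of 50 adult patients", and "Both eyes will be evaluated in this study". Before any drops, "five immediately consecutive readings will be obtained with the Eye Check tonometer", and "Each of these readings will be recorded in the Eye Check tonometer connected computer". The reference follows: "IOP measurements by a certified ophthalmic technician using the Goldmann Applanation tonometer, within 5 minutes after the use of the Eye Check tonometer". The text does not state that the five readings are per eye, although that is the likely meaning, and it does not give the number of Goldmann readings.

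The whole analysis plan is the short section Data Analysis & Statistical Considerations. Three of its sentences bear on this point:

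- "The IOP readings from the Eye Check tonometer and the Goldmann will be compared".
- "Mean IOP and standard deviation of IOP measurements using the two devices will be assessed".
- "The IOP, Standard of Measurement, number of successful readings, and performance scores will be derived".

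The section does not say whether the five readings are averaged, pooled or analysed one by one. It does not say whether the SD is taken over readings, eyes or patients, or what Standard of Measurement is. It names no paired difference, limits of agreement, repeatability statistic or variance model.

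**The concern.** The purpose of the study is to show that Eye Check measurements are comparable to Goldmann. The background argues for self-tonometry because office readings miss peaks and variations in IOP. A reader will therefore want to know two things: how well the devices agree within the same eye, and how much of any disagreement is noise in one self-reading.

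The named statistics answer neither. Mean and SD by device describe each device's distribution separately and ignore the pairing. The unstated handling of replicates also matters. Averaging five readings with independent errors removes four-fifths of the within-eye error variance before the comparison. Pooling them leaves an Eye Check SD that mixes within-eye error with spread between patients. The undefined term adds to the ambiguity: a standard error of a five-reading mean is smaller than the single-reading SD by a factor of √5 = 2.24.

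If these choices are left until the data are in, comparability could be claimed for a five-reading average and read as applying to any one self-reading.

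**Working it through.** The plan gives no SD, margin, correlation or sample-size calculation, so there is no figure of its own to reproduce. Every SD and correlation below is an assumption, in mmHg. From the documents come 50 patients, both eyes and five readings. I take the five as per eye.

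**1. Mean and SD by device do not determine agreement.** If both devices have SD 4 and correlation r, the half-width of the 95% limits is 1.96 × 4 × √(2(1 − r)).

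| r | Half-width |
|---|---|
| 0.5 | 7.84 |
| 0.7 | 6.07 |
| 0.9 | 3.51 |
| 0.95 | 2.48 |

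The SDs by device are identical in all four rows.

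**2. A pooled SD does not reveal within-eye error.** A pooled single-reading SD of 5 is compatible with a within-eye SD s_w of 1, 2 or 3, the between-eye SD being √(25 − s_w²) = 4.90, 4.58 or 4.00. The repeatability coefficient 1.96 × √2 × s_w is then 2.77, 5.54 or 8.32.

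**3. One reading against the mean of five.** Let 2.0 be the SD from all other sources of difference between the devices, including Goldmann error. With independent reading errors:

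- SD(mean of 5 − Goldmann) = √(2.0² + s_w²/5)
- SD(single − Goldmann) = √(2.0² + s_w²)
- half-width = 1.96 × SD

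| s_w | Mean of 5 | Single | Ratio |
|---|---|---|---|
| 1.5 | ±4.13 | ±4.90 | 1.19 |
| 2.0 | ±4.29 | ±5.54 | 1.29 |
| 2.5 | ±4.49 | ±6.28 | 1.40 |
| 3.0 | ±4.72 | ±7.07 | 1.50 |

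If bias is zero and differences are normal, the share beyond an illustrative 5 mmHg is 1.8% to 3.8% for the mean and 4.6% to 16.6% for a single reading.

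**4. Sensitivity to the inputs.** Now fix the SD of (mean of 5 − Goldmann) and use Var(single) = Var(mean of 5) + (1 − 1/5) × s_w².

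| SD of mean difference | Half-width, mean of 5 | Half-width, single, s_w = 1 / 2 / 3 | Wider by |
|---|---|---|---|
| 2.0 | 3.92 | 4.29 / 5.26 / 6.56 | 10% / 34% / 67% |
| 3.0 | 5.88 | 6.14 / 6.85 / 7.89 | 4% / 16% / 34% |

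The direction is the same throughout. The size runs from about 4% to 67%, depending on s_w.

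**5. Can the planned data support the separation?** Counting one eye for each of 50 patients, s_w has 50 × (5 − 1) = 200 degrees of freedom, and its 95% confidence interval is about 0.91 to 1.11 times the estimate. This assumes that all 50 pass the alignment step and that all readings succeed; fewer would widen it.

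**6. Varying numbers of successful readings.** The plan derives a count of successful readings, so the number k can differ between eyes. The variance of the mean then contains s_w² × average(1/k), and the identity becomes Var(single) = Var(mean) + (1 − average(1/k)) × s_w². A single fixed k is not valid in general.

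**The case against.** The strongest reply is that the text is brief, not wrong. Several stronger readings are tempting, and the documents do not support them.

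- *The plan reduces five readings to one IOP and one SD per device.* It does not say so. It speaks of readings being compared, and the device description in Background & Significance has the IOP derived after the measurement procedure, so one IOP per reading is possible. Reading-level analysis is not excluded.
- *The plan derives no within-eye precision figure.* Standard of Measurement is undefined, but it is listed beside the count of successful readings and could be a within-eye SD or a standard error of measurement. What stands is that it needs a definition. Even on the favourable reading, no stated step combines it with the difference from Goldmann.
- *The trial will be unable to show single-reading error.* Each reading is recorded, so the quantity can be estimated. The gap is in the prespecified analysis.
- *The main claim must rest on a single reading.* No section says home use will be one reading, and the only use described is five consecutive readings. Reporting both is sound; ranking one above the other is a preference.

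It is also fair to say that every SD here is assumed, that immediately consecutive contacts may have drifting or correlated errors, and that the wider omission is any paired agreement analysis at all. None of this removes the point: followed as written, the named statistics yield neither paired agreement nor the error of one reading.

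**Conclusion.** The concern holds as a gap in specification with a practical consequence. The plan does not state how the replicates enter the comparison, leaves one derived quantity undefined, and names only summaries by device, which cannot answer the study's question.

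If the readings are averaged, limits for one reading would be 19% to 50% wider than those reported, given s_w of 1.5 to 3.0 mmHg, 2.0 mmHg for other sources, and five successful readings with independent errors. Across the other inputs tried the range is about 4% to 67%. The shares beyond 5 mmHg need zero bias and normal differences as well, and are illustrative only. The change should be made, but nothing irreversible is lost if it is made before the data are analysed.

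**What to change.** In Data Analysis & Statistical Considerations:

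1. State that the five readings are per eye, if that is meant, and that an IOP is derived for each reading. State the number of Goldmann readings and how they are used.
2. Replace Standard of Measurement with the within-eye SD from a reading-level mixed model with patient, eye and residual terms. Label it within-session repeatability, because the readings are immediately consecutive.
3. From paired differences to Goldmann, report bias and 95% limits of agreement twice: for a single Eye Check reading and for the mean of the successful readings. Estimate both directly from the model, or use the average of 1/k where the number of successful readings varies.
4. State which of the two any claim of comparability refers to.

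The cost is a few sentences and slightly more analysis. It needs no further patients, visits or measurements. The downside is that the single-reading limits will be wider.
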